Intervention: Immediately after consenting to participate, we will provide residents a coupon for a free copy of a modified version of the Study Guide. This will allow intervention group residents to access the modified app. Participants will then receive an *alert to the clinical case of the week* on their smartphone or tablet computer (iOS or Android). On tapping this alert, the app will open to allow reading of this case and up to 5 case-related test questions. As each question is answered, participants get immediate feedback by comparing their answer with the textbook answer provided on the subsequent screen. For each case, after the final question, participants will reflect on the correctness of their answers, using a checklist with two response options, as follows: (1) My answers are (largely) correct, or (2) My answers are (largely) incorrect. If incorrect, the adaptive system will automatically send an alert to that specific case in 7 days, to promote learning by repeating its questions. Correctly answered questions will also be re-presented to participants, but via an alert to repeat that case and its questions in 14 days. These spacing intervals between repetitions were based on research findings to optimize long-term retention of learning.¹⁰ Alerts to case-related questions will be retired (no longer sent) under two conditions: once the case and its questions are answered correctly twice consecutively, or by request after three attempts.

In the appendix, we provide an algorithm to summarize this intervention.

Comparison: Residents in the control group will receive the standard version of the app at no charge, with no alerts. This version will provide the equivalent of clinical cases and test questions-on-demand.

Participants in both groups will be encouraged to answer test questions, as each university will create an alias (avatar) for healthy competition. Each alias will earn one point for each attempt to answer a set of case-related questions. Total points earned per university will be displayed as scores on a leaderboard to encourage this competition.²⁰

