What are the proposed arrangements for allocating participants to trial groups? One co-applicant (JK) will conduct a computer generated and blinded central randomization procedure of universities (clusters) to trial groups. As the unit of randomization, all Canadian universities will be stratified per the median number of residents by site, and then randomly allocated to the intervention or the control arm. This will minimize the effect of any inequality between clusters on the results. Following randomization, recruitment will begin locally as co-investigators at each site will obtain a list of their eligible residents. Consenting residents will then receive a coupon to install the app by the start date. The period from July to November 2017 will provide ample time to obtain consent. Participants will exit the study on the first day of their exam in the spring of 2019.

What are the proposed methods for protecting against sources of bias? Trial outcomes (exam scores and questions completed) are objectively assessed. Residents will be blinded to the nature of the intervention. Our consent form will not mention our research questions or the intervention. The certification exam will be scored by persons unaware of group allocation.

How will contamination be addressed? Participants will unlock the trial versions of the app using a coupon with a unique login number. We will track logins for each unique ID. With this tracking, intervention group residents will not access the version of the app destined for control group residents, or vice versa. In addition, randomization at geographically dispersed sites will limit the ability of intervention group residents to influence those allocated to the control group. Residents at different universities share no core rotations.

What are the planned inclusion/exclusion criteria? All incoming family medicine residents in Canada will be eligible. These eligible residents will be clustered within university training programs. We will exclude residents from other specialties who happen to be on rotation in Family Medicine. We will deliver the intervention from December 2017 to April 2019 (70 weeks). We will follow each resident and provide tech support.

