What are the proposed primary and secondary outcome measures? Our primary outcome will be the score on the written component of the CFPC certification exam in April 2019. Co-applicant CB is authorized by the CFPC to provide de-identified scores for each participant. We will also test the hypothesis that alerts to reinforcement of content result in greater resident engagement with test questions, as compared with control residents not exposed to alerts to reinforcement of content. Therefore, our secondary outcome will be the number, percentage and time to completion of all correctly answered questions, per case. These data will help explain the expected improvement in exam scores.

Using a study “dashboard”, we will monitor app usage over time at the group level, by examining a dynamic count of answered questions. In addition to counting attempts and correctly answered questions, the date and time of each attempt will be tracked and automatically recorded at the server. Thus, for each

case and for each participant, we will calculate a time to completion of that case. This will be defined by counting the number of days from the study start date in 2017 to the date that test questions for that case were deemed to be correctly answered.

Through a baseline questionnaire, we will collect data on potential confounders at the participant level: age, sex, Canadian or International Medical Graduate status and whether they hold a graduate degree.

What is the proposed sample size and what is the justification for the assumptions underlying the power calculations? We will have 80% power to detect an effect size of 0.4 (Cohen's d). This effect corresponds to a 4% absolute increase in score, equivalent to two additional correct exam questions. Assumptions: Clusters will provide an average of 80 residents. Given this projected number, we will consent a minimum of $8 \times 80 = 640$ residents at 8 university training sites. If residents at 12 sites are consented, we will have adequate power to detect an effect size of 0.4. These assumptions are based on pilot study findings as well as actual scores obtained by all residents in Canada on the certification exams conducted in the spring of 2015 and the spring of 2016. We detail our calculation of the proposed sample size (and the design effect) in the appendix.

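### The secondary outcome counts correctly answered questions, but the only marking described is the resident's own rating, which drives alerts in the intervention arm alone, so the arm comparison could be biased

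*Combined protocol and SAP*

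**What the plan says.** Under *What are the proposed methods for protecting against sources of bias?* the protocol says: "Trial outcomes (exam scores and questions completed) are objectively assessed".

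Under *What are the proposed primary and secondary outcome measures?* the definition is different: "our secondary outcome will be the number, percentage and time to completion of all correctly answered questions, per case". Time to completion of a case runs from the study start date to "the date that test questions for that case were deemed to be correctly answered". The same section says that the date and time of each attempt are recorded at the server.

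How correctness is decided is described only under *Intervention*. There, "participants get immediate feedback by comparing their answer with the textbook answer provided on the subsequent screen". After the last question of a case, "participants will reflect on the correctness of their answers, using a checklist with two response options": largely correct or largely incorrect. The rating has consequences. "If incorrect, the adaptive system will automatically send an alert to that specific case in 7 days"; a case rated correct comes back after 14 days. Alerts are retired "once the case and its questions are answered correctly twice consecutively, or by request after three attempts".

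Under *Comparison*: "Residents in the control group will receive the standard version of the app at no charge, with no alerts". Cases and questions are to be equivalent; the checklist is not mentioned. Leaderboard points are given per attempt in both arms, whether or not the answers are right.

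Under *What is the proposed type of analyses?* the arms are compared on time to correct completion by a Cox model with a sandwich covariance, adjusted for potential confounders.

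**The concern.** The objectivity statement speaks of questions completed, while the outcome to be analysed is questions correctly answered. The server makes the time stamp objective. It does not make the verdict on correctness objective if the resident enters that verdict after seeing the textbook answer.

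Self-rating that was equally generous in both arms would mainly blur the outcome. Here the rating has an effect in one arm only. An intervention resident who rates a case correct gets a longer interval and, after two such ratings in a row, no further alerts for it. A control resident receives no alerts, so a rating there triggers none. That gives a reason for rating behaviour to differ by arm.

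The protocol uses this outcome to test whether alerts raise engagement and to help explain the expected gain in exam scores. A difference in rating habits could be read as a difference in engagement or learning, or could hide a real one. Covariate adjustment and a sandwich covariance deal with confounding and clustering. Neither removes outcome misclassification that differs by arm. The text describes no independent marking, validation sample or sensitivity analysis for the rating.

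**Working it through.** The protocol gives no figure to reproduce on this point. The check has three parts.

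**1. What generates the event in each arm**

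| | Intervention | Control |
|---|---|---|
| Answer attempts | logged with date and time | logged with date and time |
| Verdict on correctness | resident's checklist | not stated |
| Effect of rating incorrect | alert in 7 days | no alert |
| Effect of rating correct | alert in 14 days; two in a row retire the case | no alert |
| Leaderboard point | per attempt | per attempt |

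The first and last rows are the same in both arms. The three between them differ or are unstated. The text also leaves open who deems a case correct and whether one or two correct ratings count as completion.

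**2. How strong the incentive is**

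The app has 70 cases. If every alert is acted on:

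- Rating correct each time takes two attempts per case, so one repeat alert: 70 × 1 = 70.
- Rating incorrect each time takes at least three attempts before retirement can be requested, so two repeat alerts: 70 × 2 = 140.

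The gap between these two extremes is at least one alert per case, over a 70-week intervention. The incentive is real but modest.

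**3. What unequal rating would do to the hazard ratio**

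All rates here are assumptions; the documents give none. Let *t* be the proportion of case attempts truly correct, equal in both arms so that there is no true effect. Let *f* be the share of wrong attempts rated correct. Then

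P(rated correct) = *t* + (1 − *t*) × *f*.

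With *t* = 0.60:

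- Control, *f* = 0.10: 0.60 + 0.40 × 0.10 = 0.64.
- Intervention, *f* = 0.30: 0.60 + 0.40 × 0.30 = 0.72.

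If cases are attempted at the same constant rate in both arms, the event rate is the attempt rate times P(rated correct), and the attempt rate cancels:

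HR = 0.72 / 0.64 = 1.125.

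The result depends on the model. If 0.64 and 0.72 are instead read as the proportions of cases rated correct by a common date, under proportional hazards,

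HR = ln(1 − 0.72) / ln(1 − 0.64) = (−1.273) / (−1.022) = 1.25.

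By this second formula, with control held at *f* = 0.10 and *t* varied from 0.40 to 0.70:

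| *f* in intervention | Apparent HR |
|---|---|
| 0.10 | 1.00 |
| 0.20 | 1.09 to 1.19 |
| 0.30 | 1.19 to 1.41 |
| 0.50 | 1.45 to 1.95 |

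With equal *f* the apparent effect vanishes, so here it comes entirely from the difference in rating. The formula covers over-claiming only. If intervention residents instead rated correct answers as incorrect in order to get repeats, the ratio would be pulled the other way. No rate for that is assumed here.

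**The case against.** Several objections have force.

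- **The sentence on objectivity is not false as written.** It names exam scores and questions completed, and both can be measured objectively. This stands. The defect is that the defined outcome is correctness, which that sentence does not cover.
- **The link from checklist to outcome is an inference.** The outcome is a count of questions, while the checklist gives one verdict on a case of up to five questions, and the text does not say who deems a case correct. This also stands, but no other marking is described. The questions imitate short-answer problems, and no automatic or third-party scoring is mentioned. The intervention algorithm sits in an appendix that is not available and may say more.
- **The incentive is weak and may run both ways.** Leaderboard points reward attempts, retirement on request after three attempts is possible, and residents preparing for a high-stakes exam may welcome repeats. This limits any claim about size or direction. It does not show that rating is the same in both arms.
- **The illustration holds attempt rates equal, though alerts are meant to raise them.** True. The share of any observed hazard ratio due to rating could not be separated from a real effect on attempts, which is itself a reason to measure the two apart.

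A reader might also infer that the secondary outcome does not exist in the control arm because the checklist appears only under *Intervention*. The documents do not support that. The outcome and analysis sections plan to count correct answers without limiting this to one arm, and they compare the arms on it, so they presuppose capture in both. Silence justifies asking how it is done, not concluding that it is absent.

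**Conclusion.** The concern holds for the secondary outcome. As far as the text shows, correctness is self-rated, the rating has alert consequences in one arm only, and its capture in control is unspecified. The Cox comparison, and the number and percentage correct so far as they rest on the same rating, could therefore carry misclassification that differs by arm.

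The size is illustrative only: an apparent hazard ratio of about 1.13 with no true difference, given 60% truly correct in both arms, 10% v 30% of wrong attempts rated correct, and equal constant attempt rates. Other assumed rates and the other formula give other values.

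A reader might go further and conclude that the comparison is biased in favour of the intervention. The documents establish neither the direction nor the size, only that the design leaves room for such bias. The primary outcome, scored by persons unaware of allocation, and its confirmatory test are not touched.

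**What to change.** - **Outcome and analysis sections.** Test the engagement hypothesis on the first server-logged completion of each case, meaning that all its questions are answered, defined identically in both app versions. Use this event in the Cox model.
- **Correctness.** Keep it as a secondary measure labelled self-rated, captured on the same checklist screen in both versions and interpreted with that limit. State whether one or two correct ratings count as completion.
- **Bias section.** Confine the objectivity statement to exam scores and server-logged completion.

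The cost is small: wording in three sections, and one checklist screen to be confirmed or added in the control build. The app is already being modified for the trial and attempts are already time-stamped. Control ratings not captured during the trial could not be recovered later, so this should be settled before launch. The downside is that completion says less about mastery than correctness does, which is why the self-rated measure is kept beside it.

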priority topic. McGill residents were given the same app but received no alerts, providing them with information on demand. After 100 days, we performed an interim analysis on the number of opened pages in the app, using priority topics as pairs. Intervention group residents opened more pages of information, per priority topic (15.7 ± 21.8 vs 9.1 ± 14.4 , $p < 0.0003$). These findings are promising. (4) There are no studies of spaced education in the context of Family Medicine training. (5) Our ability to conduct the proposed work is enhanced through a partnership with the CFPC. Thus, our proposed research is feasible, innovative and supported by pilot study findings.

Research question

Among family medicine residents, does enhanced feedback through an app providing alerts and test questions (spaced education), compared to the same app without alerts and enhanced feedback (no spaced education), improve competence as measured by the certification examination?

Design: We propose a cluster randomized controlled trial. For this trial, a medical school is a natural cluster of residents, with no crossovers. This study will be registered at clinicaltrials.gov and conducted to the highest standards. To ensure good reporting, our main manuscript will include all essential elements in accordance with standards articulated in the CONSORT statement.²⁹ The trial will be coordinated by RG who will chair the steering committee comprised of co-applicants. Research assistants supervised by co-applicants and collaborators will manage the trial at each site. First-year residents will enter the trial in December 2017.

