What are the planned trial interventions? We will take advantage of a popular commercial app containing 70 unique clinical cases with test questions that simulate the short answer problems on the certification examination. The FM Study Guide (hereafter the 'Study Guide') is a mobile device based platform for residents to test their knowledge of typical clinical cases covering Priority Topics in Family Medicine. Please see screenshots at <http://www.familymedicinestudyguide.com/>. Created in 2015 as a non-profit venture by co-applicant DL, 100% of app revenue is donated to charities or used to ensure app sustainability. Through the Study Guide, residents interact with test questions. These interactions can last 5 minutes or less, and therefore fit easily into the lives of busy residents. For this trial, we will modify the app to provide a weekly alert as well as adaptive reinforcement of content based on test question performance. This will allow intervention group residents to take full advantage of both the spacing and the testing effect. However, both versions of the app will provide equivalent cases and test questions to intervention and control groups.

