What is the planned recruitment rate? What evidence is there that the planned recruitment rate is achievable? With support from co-investigators and collaborators, each university will recruit at least 80% of their residents. The evidence for this comes from our pilot study, in which we consented more than 80% of residents at two university sites in Quebec and Ontario. This is not surprising; residents perceive a need for an app based on Priority Topics to help pass a high-stakes exam. We will report the number of residents eligible for participation in both study arms, their flow through the study and losses to follow up using a CONSORT-style flow diagram. While we anticipate a small loss of consenting residents to follow up, for example at McGill just two residents transfer out, on average per year.

What is the proposed type of analyses? We will follow the guidelines of the CONSORT statement for clustered randomized trials and recommendations for their analysis when presenting and analysing our data.²⁹ The primary efficacy analysis will be based on the intention-to-treat population i.e. all study participants will be analysed as randomized. The primary statistical analysis will evaluate the difference in mean exam scores between residents in the intervention and control groups using a linear mixed effects model. The mixed model will incorporate study site as a random factor and the following fixed factors (as presumed predictors of exam score): study group assignment (control / intervention), age, sex, completion of a graduate degree, and IMG status. The estimated fixed effects will be reported along with 95% confidence intervals. Confirmatory assessment of the primary endpoint will be based on the confidence interval for the fixed effect estimate of "study group", implying a two-sided level of significance (against the null hypothesis of no effect) of 0.05.

Regarding the secondary outcome of time to correct completion of test questions: For each resident, a mean time to event (with confidence intervals) will be calculated separately for each clinical case in the app, averaged and then compared across groups. These data will be described using a Kaplan-Meier curve. To account for clustering while adjusting for potential confounders, we will use a Cox regression model with a sandwich covariance structure. In the adjusted model, we will compare the hazard for this secondary outcome, between intervention and control groups, as of April 2019.

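### Engagement is compared between arms only on time from study start, which mixes how many cases are completed with when; number and percentage completed have no stated analysis

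*Combined protocol and SAP*

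**What the plan says.** The section on primary and secondary outcome measures says the trial will "test the hypothesis that alerts to reinforcement of content result in greater resident engagement with test questions", and from this it derives that "our secondary outcome will be the number, percentage and time to completion of all correctly answered questions, per case". Time is defined case by case, by "counting the number of days from the study start date in 2017 to the date that test questions for that case were deemed" correct. The origin is the same for every case, whatever the date on which the case was first alerted or opened. The section adds that these data should help to explain the exam result.

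The section on the type of analyses has one paragraph on the secondary outcome, and it deals with time only. It gives two comparisons and a Kaplan-Meier curve:

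- a between-arm comparison of averaged times, described as follows: "For each resident, a mean time to event (with confidence intervals) will be calculated separately for each clinical case in the app, averaged";
- an adjusted Cox model with sandwich covariance, in which "we will compare the hazard for this secondary outcome, between intervention and control groups, as of April 2019".

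No effect measure, test or clustered model is given for the number or the percentage. The only other stated use of counts is group-level monitoring on a dashboard.

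The trial-interventions section describes "a popular commercial app containing 70 unique clinical cases with test questions". Intervention residents receive an "alert to the clinical case of the week", with repeat alerts after 7 or 14 days, over a 70-week delivery period. Control residents have equivalent cases on demand and no alerts.

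**The concern.** Two of the three named components, and the two closest to volume of engagement, have no planned between-arm analysis. The engagement hypothesis is therefore left to time from study start.

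On that clock the hazard ratio depends on two things: what share of cases a resident completes, and where in the 70 weeks the completions fall. Alerts act on both. In the control arm the second is each resident's own choice. Two arms that complete the same share can therefore differ in hazard. A hazard ratio below 1 could be read as less engagement, and one above 1 as more, when only the timing differs.

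The averaged mean time has a further gap. A case that is never completed has no completion date, and the text gives no rule for it. Averaging completed cases only selects on something that happens after randomisation.

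What is at stake is the explanation of the exam result, and the freedom to choose an analysis of number and percentage after the data are seen.

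**Working it through.** **Plan's own figure.** There is none to reproduce. The plan states no power, event count or hazard ratio for this outcome; its 80% power refers to the exam score.

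**Inputs from the protocol.** 70 cases; a weekly case alert; 70 weeks = 490 days; control cases on demand; 80 residents per site, with 8 and 12 sites both mentioned; pilot page counts per topic after 100 days of 15.7 with alerts against 9.1 without.

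**Assumed.** One new case alerted per week; the completion shares; the timing patterns; the site correlation in step 5.

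**1. Pacing.** With case *k* first alerted on day 7(*k* − 1), the mean first-alert day is 7 × (0 + 1 + … + 69)/70 = 7 × 34.5 = 241.5. The last case is first alerted on day 7 × 69 = 483 of 490.

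**2. Control timing matched to the pilot.** The pilot ratio is 15.7/9.1 = 1.725. At 60% final completion, an alert-following arm has completed about 60% × 100/490 = 12.2% of cases by day 100. Controls would then have completed 12.2%/1.725 = 7.1%. A completion-time distribution (t/490)^1.348 gives approximately this, with mean 490 × 1.348/2.348 = 281 days. It treats the whole pilot ratio as timing. The pilot used a different app and counted pages opened, so it is only a guide.

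**3. Hazard ratio.** Simulation of 2,000 residents × 70 cases per arm, uncompleted cases censored at day 490. Intervention completions fall at the alert day plus an exponential lag with mean 4 days.

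| Control timing | Mean control day | HR, 60% vs 60% | HR, 60% vs 40% | Control share at which HR = 1 |
|---|---|---|---|---|
| Early (exponential, mean 90, truncated at 490) | 88 | 0.74 | 1.42 | 50% |
| Uniform on 0–490 | 245 | 1.00 | 1.76 | 60% |
| Late (490 minus exponential, mean 45) | 445 | 1.44 to 1.45 | 2.31 | 77% |
| Pilot-like | 281 | 1.07 | 1.84 | 62% |

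The last column shows the mixing. With early controls, a real ten-point advantage (60% vs 50%) gives a hazard ratio of 1. With late controls, a 17-point disadvantage (60% vs 77%) does.

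Sensitivity:
- If half of the intervention completions follow control-type timing, the equal-completion hazard ratios move to 0.85, 1.00, 1.19 and 1.02.
- With a 7-day lag and 80% completed in both arms, they are 0.53, 1.00 and 1.70 for controls working early (mean day 60), evenly, or late (mean day 430).
- In that second setting, 90% vs 70% in favour of the intervention gives 0.92 with early controls and 3.07 with late ones.

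**4. Averaged mean time, 60% vs 40% completed.**
- Early controls, completed cases only: 245 vs 88 days.
- Early controls, uncompleted cases set to day 490: 0.6 × 245 + 0.4 × 490 = 343 vs 0.4 × 88 + 0.6 × 490 = 329 days.
- Either way the arm that completes more looks slower. The reversal needs a control mean below 245 days on the first rule. On the second, 0.4*m* + 294 = 343 gives *m* = 122.5 days.
- Pilot-like controls: 245 vs 281 and 343 vs 406 days, with no reversal.

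**5. Behaviour of the tests at equal 60% completion.** 12 sites of 80, assumed site ICC 0.027 and 0.148 (logit scale), 400 trials per cell, two-sided 5%. The site-clustered Cox test rejects in 95.5% and 46.8% of trials (early), 5.5% and 3.5% (uniform), 99.5% and 61.5% (late), 16.5% and 5.0% (pilot-like). An unadjusted t-test on site-mean percentage completed rejects in about 3% to 6%.

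**The case against.** Time to completion is itself a named outcome, and spacing is the point of the intervention, so when residents work is part of the intended effect. A common origin preserves the randomised comparison. All of this stands, and the hazard ratio is valid for the total effect on timing.

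A reader might infer from step 5 that the Cox test has an inflated false-positive rate. It does not follow. In the early and late scenarios completion timing truly differs, so the Cox null is false and rejection is correct. The error comes only if the result is read as volume of engagement.

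A reader might also infer that the clock is biased against the intervention because alerts release cases gradually. The documents do not support a direction. They do not give control timing. The pilot finding that "Intervention group residents opened more pages of information, per priority topic" does not suggest controls who work early. Both arms face the same exam and share the leaderboard incentive. One new case per week is inferred, the algorithm is in an appendix not seen here, and nothing bars opening a case before its alert. The large distortions need one-sided behaviour that is assumed.

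Two further points stand. The follow-up to April 2019 implies that uncompleted cases are censored in the Kaplan-Meier and Cox analyses, so only the averaged mean is undefined. And the self-rating checklist is described under the intervention only. Unless the control app rates correctness in the same way, a percentage completed is not comparable either.

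None of this supplies an analysis for number or percentage.

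**Conclusion.** The concern holds in a limited form. That number and percentage have no stated between-arm analysis, and that the averaged mean time is undefined for uncompleted cases, follows from the text without any simulation.

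That the hazard ratio does not isolate engagement follows from the common time origin. How far it could mislead is uncertain. At equal 60% completion it runs from about 0.74 to 1.45 over the assumed control timings and is about 1.07 with pilot-like timing. These values rest on inferred weekly pacing and on residents completing cases soon after alerts. A completion gap usually shows in the expected direction, but not always (0.92 at 90% vs 70% in one setting).

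The plan should be changed, but the matter is confined to an explanatory secondary outcome. The confirmatory exam-score analysis is not affected.

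**What to change.** 1. Make the between-arm test of engagement the proportion of the 70 cases completed by exam day, derived per resident from the server log. This is a derived measure: the plan speaks of correctly answered questions per case. Use a model with a site random effect, the covariates planned for the primary outcome and a small-sample correction for the number of sites, or a site-level analysis. The 3% to 6% in step 5 was obtained with a site-mean t-test and does not vouch for the mixed model.
2. As a precondition, define completion identically in both arms, including whether one correct attempt or two consecutive ones are required, and state that correctness is self-rated. Report cases attempted at least once as the supporting measure that does not depend on self-rating. Give total attempts descriptively only, since the repeat alerts raise them in the intervention arm.
3. Drop the averaged mean time.
4. Keep the Kaplan-Meier curve and the Cox model, with uncompleted cases censored at exam day, as the analysis of completion timing, and state that the hazard ratio is not a measure of volume of engagement.

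Cost: a short addition to the analysis plan, a little more analysis work and a narrower reading of the hazard ratio. Attempts and correct answers are already logged with date and time, so no new data are needed provided the control app records correctness in the same way; the text does not confirm this. One limit remains: repeat alerts after an answer rated incorrect give intervention residents extra chances to rate a case correct, which is why cases attempted should stand beside the proportion completed.
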